2. RESEARCH PLAN

Purpose of Study:
To compare scar infiltration with 0.5-1% Lidocaine at a dose of 3 mg/kg (max dose 300 mg) or scar deactivation with acupuncture surface release technique to determine which is more effective in reducing pain in adult patients with chronic, post-surgical pain related to the site of incision after low transverse Cesarean section compared to standard of care physical therapy with the McKenzie Method.
Hypotheses, Research Questions, or Objectives:

 • Objective 1: Compare whether a scar infiltration protocol with Lidocaine is more effective than scar deactivation with acupuncture surface release technique at improving pain in adults with chronic, post-surgical pain related to low transverse Cesarean section incision. • Null Hypothesis 1: 0.5-1% Lidocaine at a dose of 3 mg/kg (max dose 300 mg) does not reduce pain outcomes acutely and over time. • Null Hypothesis 2: Scar deactivation with acupuncture surface release technique does not reduce pain outcomes acutely and over time. • Alternative Hypothesis 1: 0.5-1% Lidocaine at a dose of 3 mg/kg (max dose 300 mg) reduces pain outcomes acutely and over time. • Alternative Hypothesis 2: Scar deactivation with acupuncture surface release technique reduces pain outcomes acutely and over time.
Significance:
According to CDC 2015 data, 32% of all births are delivered via Cesarean section ¹ . In patients who undergo Cesarean section, studies estimate 7-18% will experience chronic post-operative pain at the site of their incisional scar ² . These statistics indicate that up to 1 in 6 out of every pregnancy is at risk of developing postoperative pain with an increased risk with each subsequent Cesarean section, and a significant portion of these members will seek care in the primary care clinic.
Military Relevance:

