In 2016, the Department of Defense employed 1,288,596 active duty service members, of which 15.9% were women ³ . This age range is consistent with peak childbearing age, which extrapolates to a large portion of the female active duty force with the potential to have children during their military careers. Determining whether Scar infiltration or scar deactivation is more effective treatments for the reduction of chronic, post-surgical low transverse Cesarean section pain in military beneficiaries would result in less: lost duty days, profiles, and physical fitness testing exemptions in our active duty population, as well as an improved quality of life for all DoD beneficiaries. Scar infiltration is a technique using high dose and high volume lidocaine to infiltrate the scar. Scar infiltration uses 40cc to 60cc of 0.5% to 1% lidocaine, which is injected throughout the scar with a goal of 3-4mg/kg per injection. Typically a series of 4 to 5 injections. Scar deactivation is a technique when acupuncture needles are inserted into the skin surrounding the scar and are left in place for approximately 20 minutes and then removed. This can be repeated multiple times.

Background and Review of Literature:

Existing Knowledge: The etiology of chronic, post-surgical abdominal wall and/or pelvic pain after Cesarean section has multiple hypotheses. These possible sources include development of intra-peritoneal adhesions restricting fascial planes, anterior cutaneous nerve entrapment, and disruption of the autonomic nervous system within the intracellular fluid matrix known as an “interference field”^{2,4,5,6,7}. While there is not a clearly established and widely accepted pathophysiological cause to this post-operative pain, studies have estimated that between 7-33% of patients experience chronic peri-incisional pain after Cesarean section with Pfannenstiel incision – a type of abdominal surgical incision that allows access to the abdomen and the most common method for performing Cesarean sections today – defined as pain persisting beyond the period of expected healing, approximately 3 months^{2,7}.

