Gaps in Knowledge: Management of chronic peri-incisional pain after Cesarean section requires an extensive workup including laboratory testing (CBC, ESR, Urinalysis, STI testing) and imaging (transvaginal ultrasonography and abdominal CT) to rule out organic causes^{5, 6, 8}. Once a visceral etiology from postoperative pain has been excluded, there is not a well-established guideline dictating standard of care, however treatment can include analgesics such as Acetaminophen or Non-Steroidal Anti-inflammatory Drugs, and in refractory cases suggestive of neuropathic pain Tricyclic Antidepressants, Gabapentin, Pregabalin, and Serotonin-Norepinephrine Reuptake Inhibitors can be used^{5, 6, 8}. If medicinal therapy fails to manage symptoms, consultation for pain management specialists and/or surgical evaluation is often considered^{5, 6, 8}.

Scar deactivation is used as standard of care for treatment and resolution of scar associated pain in patients with a history of Cesarean section by medical acupuncturists, both abdominal and/or low back pain that began after the cesarean section. Scar infiltration with lidocaine has been used in numerous clinical settings, masquerading under different names. Referred to as “Neural Therapy” in Germany, the technique of injecting short-acting local anesthetic into the dermal subcutaneous junction of scar tissue has been widely applied; however there is limited readily available clinical trial evidence supporting its reported effectiveness^{9, 10, 11}. Theoretically, it is postulated that the anti-inflammatory effects of local anesthetics play a role in mitigating the autonomic nervous system disruption of “interference fields” caused by scar tissue^{9, 10, 11}. Local anesthetics promote anti-inflammatory activity through a variety of mechanisms including reversibly inhibiting leukocyte adhesion by interfering with the action of integrins and leukocyte adhesion molecule-1, limiting leukocyte migration, reversible inhibition of phagocytosis, inhibition of phospholipase A2, inhibition of prostaglandins, inhibition of thromboxane release, inhibition of leukotriene release, inhibition of histamine release, reduction in free radical formation, inhibition of cytokine release of IL-1 β , IL-8 and TNF- α ^{12,13}. Additionally, Lidocaine injection is proposed to alleviate nerve entrapment within fascia through hydrodissection, a technique being effectively utilized in the management of carpal tunnel syndrome¹⁴.

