3. RESEARCH DESIGN AND METHODS

Research Design and Methods:

Active duty members and DoD beneficiaries, age 18 years of age or older, meeting the inclusion/exclusion criteria will be offered an opportunity to participate. They will be recruited from the clinics located at Nellis AFB and Scott AFB. All of the below items are research-related unless marked as 'standard of care':

Pre-Eligibility review: Subjects who responded to advertisements or recruitment letters or have given their permission to be contacted will be approached by a study staff member to discuss the subject's interest in the research study and to receive a pre-eligibility screening for study participation. The attached "Pre-Eligibility Review Script" will be used and response will be recorded. If the subject is interested in participating in the study, the study staff member will schedule a screening visit while the subject waits on the phone or in-person, in order to confirm the schedule appointment with the subject. Following the pre-screening procedure, the script will be shredded.

Screening Visit:

- Obtain and document signed Informed Consent document and HIPAA Authorization.
- Review past medical history to verify the inclusion/exclusion criteria including previous encounter, medication list (including analgesic medication currently taking), co-morbidities, demographics, and problems list.

- Record date of birth, age, gender, race, ethnicity, DoD ID, current email address, height (inches), weight (in pounds-not stated weight), obstetrical history, history of relevant pain and interventions.
- Instruct subjects to discontinue any current acupuncture treatment at the onset of entering the study. It is theorized that any acupuncture treatment can have a positive or a negative effect on treatment response regardless of the technique or treatment indication.
- If the subject is an active duty member, we will ask:
 - Have you or are you currently on a fitness restriction for this condition.
 - If so, what are/were the dates of the restriction?

Randomization:

- Subjects will be randomized into one of three research-related treatment groups using block randomization with repeated measures:
 - **Group 1: Scar Deactivation Surface Release Technique protocol:**

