This study will follow all FDA requirements for the safe use of the acupuncture needles. The Food and Drug Administration (FDA) regulates acupuncture needles (see 21 CFR 880.5580) as a class II medical device, because they are intended for use in the cure, mitigation, treatment, or prevention of disease in man or are intended to affect the structure or function of the body of man. The needles being used are Spring Ten 0.30x40mm Acupuncture needles (see figure 1 below), which are exempt from premarket notification by the FDA for use in acupuncture and will be used in accordance with their FDA approved labeling.

a. Interventions and Observations:

Patient and Observer Scar Assessment Score (POSAS): Scar evaluation tool which has been shown to be appropriate for evaluation of linear scars, such as the Pfannenstiel incision, with good reliability and internal consistency. This scale evaluates for pain and itching at the scar site, change in color of the skin, change in stiffness or thickness of the scar, change in irregularity of the scar and overall assessment of change in the scar.

Secondary Outcomes:

- Reduction in the POSAS score
- Reduction in related symptoms including
 - dyspareunia,
 - decreased libido, or
 - Seemingly unrelated symptoms.

b. Setting:

Female (DoD beneficiaries) age 18 years or older meeting the inclusion criteria will be offered an opportunity to participate at Scott AFB, Scott AFB O'Fallon Family Medicine Residency Clinic located at [name] and Nellis AFB.

c. Date(s):

March 2019-May 2022

d. Subjects:

Female DoD beneficiaries meeting the inclusion criteria will be offered an opportunity to participate at Scott AFB and Nellis AFB. No other special populations (e.g., children, military basic trainees, prisoners, detainees) will be recruited.

e. Inclusion/Exclusion Criteria:

Inclusion Criteria	
 Female DoD beneficiaries age 18 years or older 3 months or greater postpartum with abdominal and/or back pain starting after low transverse Cesarean section scar. If subject has had prior Scar Deactivation with Surface Release Technique for cesarean section scar they must have completed a washout period of 12 weeks or more.

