Exclusion Criteria	
 Pregnant Prior Scar Deactivation with Surface Release Technique for cesarean section scar within the last 12 weeks. Ever had Prior Scar Infiltration with Lidocaine for cesarean section. Active cellulitis surrounding scar

	
 Revision of Cesarean section scar Vertical incision or emergent Cesarean section
--	---

f. Source of Research Material:						
Will you be using private information in this study?		 Yes				
If Yes,  protected health information (PHI) held by a covered entity						
Use of identifiers with private information						
Identifiers to be Used?	Column A Looked at by research team	Column B Recorded on enrollment log, subject list, or key list	Column C Recorded on data collection tool (survey, spreadsheet, etc.)	Column D Recorded on specimen containers	Column E Shared w/ others not on research team	Column F Stored after study ended
NONE						
Names						
Study codes linked to individuals' identities using a key only accessible by the researcher						
Phone/Fax Numbers						
E-mails						
DoD ID#						
Coding Plan?						

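### The three months in the inclusion criterion count time since delivery, not duration of pain, and the criterion asks for no link to the scar, so it can admit women without the chronic incision-related pain named in the purpose.

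*Combined protocol and SAP*

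**What the plan says.** Section 2 (Purpose of Study) names the target population as "adult patients with chronic, post-surgical pain related to the site of incision after low transverse Cesarean section". Under Existing Knowledge, the same section describes chronic peri-incisional pain after a Pfannenstiel incision as "defined as pain persisting beyond the period of expected healing, approximately 3 months". That is a duration of pain.

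Section 3e (Inclusion/Exclusion Criteria) admits women who are "3 months or greater postpartum with abdominal and/or back pain starting after low transverse Cesarean section scar". The exclusions are pregnancy, recent scar deactivation, any earlier lidocaine infiltration of the scar, active cellulitis, scar revision, and "Vertical incision or emergent Cesarean section". None concerns how long the pain has lasted or what causes it.

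The Screening Visit records "obstetrical history, history of relevant pain and interventions" but attaches no eligibility threshold to it. The Gaps in Knowledge text says that managing this condition needs a work-up "to rule out organic causes", but no such step appears in the criteria or at screening. The same text counts as scar-associated "both abdominal and/or low back pain that began after the cesarean section".

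Section 6 (Outcome Measures) makes reduction in the DVPRS the primary outcome, with a goal of 50%. It describes a 0 to 10 rating and names no body site, index pain or recall period.

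**The concern.** The trial sets out to answer a question about chronic pain related to the incision, but its entry rule does not require chronic pain. Being 3 months postpartum guarantees 3 months since surgery and says nothing about how long the woman has hurt. Back pain alone is enough, and any onset after the section qualifies, even if it is recent and has another cause.

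Two things are at stake. The first needs no assumption: the stated conclusion would cover a population narrower than the one enrolled. The second depends on who enrols. Recent pain may resolve in every arm over 20 weeks. Pain unrelated to the scar may not respond to treatments aimed at the scar. Either would make the results harder to read.

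**Working it through.** **Wording, element by element**

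| Element | Purpose and background (section 2) | Criteria (section 3e) |
|---|---|---|
| Duration | Chronic; pain lasting about 3 months | 3 months since delivery; no minimum for the pain |
| Onset | Post-surgical | Any time after the section |
| Site | Purpose: related to the incision; back not named. Background: abdominal or low back pain | Abdominal or back pain, alone or together; not limited to the low back |
| Link to scar | Required by the purpose; stated in the background | Not required |
| Other causes | Background: work-up needed | Not excluded |

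**Test case.** Take a woman 12 months after a low transverse, non-emergent section who has had back pain for one week.

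1. Time since delivery: 12 months is at least 3, so she passes.
2. Site: back pain alone is enough, so she passes.
3. Onset: after the section, so she passes.
4. Exclusions: none of those listed turns on pain duration or cause, so she is not removed.

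She is eligible, but her pain has lasted one week against the roughly 3 months that the protocol itself uses to mark chronic pain.

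**Illustration of dilution (context only).** Section 6 states a power of 0.95 at alpha 0.05 with 45 subjects for post hoc tests such as change over time within a treatment group. It does not name the test. One reconstruction fits:

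- n per arm = 45 / 3 = 15, assuming equal allocation.
- Effect d = 1 SD. For the DVPRS, section 6 uses the SD of 2.4 as the effect size; the SD of the change is taken to be the same.
- Two-sided paired t-test with 14 degrees of freedom and noncentrality d × √15 = 1 × 3.873 = 3.873.
- Power = 0.949, which agrees with the stated 0.95.

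Now suppose a share q has pain that does not respond, and the SD is unchanged. The mean change becomes (1 − q) × 2.4, and d becomes 1 − q.

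| q (assumed) | Mean change | Noncentrality (1 − q) × 3.873 | Power |
|---|---|---|---|
| 0 | 2.40 | 3.873 | 0.949 |
| 10% | 2.16 | 3.486 | 0.899 |
| 20% | 1.92 | 3.098 | 0.821 |
| 30% | 1.68 | 2.711 | 0.713 |

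The documents give no value for q, so the table shows sensitivity, not an estimate. It also models non-response only. Recent pain that resolves by itself would enlarge the change within each arm while narrowing the difference between arms.

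**The case against.** The strongest reply is that back pain was admitted on purpose. The purpose speaks of pain related to the incision, which is not the same as pain located at it. The background treats low back pain that began after the section as scar-associated, and section 3 lists even seemingly unrelated symptoms among the secondary outcomes. This stands. A reader might infer that admitting back pain is simply a mistake, and the documents do not support that. What remains is narrower: the criterion drops both the restriction to the low back and the association with the scar, and the purpose never mentions the back.

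A second reply concerns the DVPRS. A reader might infer that subjects rate their pain in general. The protocol text names no index pain, but section 12 lists the DVPRS form and Procedure Instructions as attachments, and these were not available. The expectation questions at Visits 1 and 5 do name chronic pain related to the Cesarean section. They are not DVPRS instructions, but they show that the index condition is put to subjects. The supportable statement is that the protocol text does not say which pain is rated.

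A third reply is that any loss of power is hypothetical. That is correct. One could also run the dilution on a single two-sample t-test between arms of 15, where a 1 SD difference starts from a power of 0.753. That starting value is not a protocol figure, the planned analysis is a repeated-measures model, and the gap between 0.753 and 0.95 is a separate matter. It should not be read as a consequence of the eligibility wording.

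None of these replies touches the duration point. The pain history taken at screening has no threshold attached, so it does not close the gap.

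**Conclusion.** The point holds for duration on the text alone. The protocol defines chronic pain by how long the pain has lasted, the criterion measures time since delivery, and nothing else in the criteria or at screening supplies the missing requirement. The criterion also lacks the link to the scar that the purpose claims. A conclusion about chronic incision-related pain would therefore not describe every eligible woman.

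For back pain, the finding is an inconsistency between purpose, background and criterion that must be reconciled. For the DVPRS, it is an omission from the protocol text that an attachment may already fill.

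The numerical consequence is unknown. The fall from 0.95 to about 0.90, 0.82 and 0.71 rests on an assumed 10%, 20% or 30% of non-responders, an unchanged SD, and a reconstructed paired test. Even the direction of the effect on a comparison between arms is not settled: back pain unrelated to the scar might respond differently to McKenzie physical therapy, which is built around position and movement. The change is worth making because it is cheap and lets the trial answer its own question.

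**What to change.** 1. Reword the inclusion criterion with the protocol's own definition: pain present for at least about 3 months that began after the low transverse Cesarean section.
2. Make the purpose, background and criterion describe one population. Either widen the purpose to name back pain beginning after the section, or bring the criterion into line with the scar-associated pain described in the background and purpose.
3. Record the site of the qualifying pain at screening (scar or abdomen, back, or both). State in the protocol text that the DVPRS rates that pain at every visit, and over what recall period. If the attached form or Procedure Instructions already say this, cite them.

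The cost is a wording amendment and one screening item. Some candidates with recent-onset pain would have to wait, which may slow accrual slightly. If the sponsor narrows the criterion instead of widening the purpose, the loss could be larger: confining entry to pain at the incision itself would remove a group that the background deliberately includes, against a target of 60 women at two sites.

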4. HUMAN SUBJECT PROTECTION

Recruitment and Consent Processes:

All potentially eligible patients will be offered an opportunity to participate. Primary Care Manager (PCM) referrals, with the patient's oral or written authorization, and posted advertisements will be utilized for recruiting subjects to the study. Some patients may be patients of the PI or AI; however, they will have another study staff recruit their patients to prevent any misconception of coercion or undue influence. When a potential subject is identified by the treating PCM, the patient will either be provided a contact number to the Research Staff, the Research Staff will be given the potential subjects contact information by the PCM, or the Research Staff will speak with the patient directly. It is not standard of care to perform this type of acupuncture on pregnant women.

Consent Processes:

Informed Consent and HIPAA authorization will be sought in advance of any screening and study-related procedures from each prospective study subject and appropriately documented in accordance with 32 CFR 219.117. Potential candidates will be notified about the study either through posted advertisements or by their healthcare provider and will be given the opportunity to consent by one of the referred study coordinators. The study coordinator will provide a written copy of the Informed Consent Document (ICD). The subject may decline to consent without prejudice. At the subjects' discretion, they may take the ICD home to discuss further with family members or another physician, prior to making a decision. If they decide they are interested in participating in the study, they can contact the research department. If the subject consents, a copy of the signed ICD and HIPAA Authorization Document will be given to the subject. No vulnerable populations are included in this research study. Subjects who cannot provide Informed Consent will not be allowed to participate. No Legally Authorized Representatives (LAR) will be utilized. Each subject will be asked to place their de-identified research data into the "Nellis Acupuncture Research Data Repository (FWH20140048H) for future research. If the subject does not give their authorization, then the de-identified research data will be destroyed no later than at 3 years after closure of the study.

Recruiting Service Members	Will you be recruiting service members in a group setting?	 Yes	 No
----------------------------	--	------------------------------	--

Participation Compensation: Subjects will not be paid for participation in this study.

Assent Process: N/A

Benefits:

Subjects may experience an improvement in pain in both the treatment groups; however, this is not a guarantee.

Risks:

The potential risks to participate in this study are minimal. The risks associated with participating in this research study include:

Acupuncture Risks:

- Likely and not serious:
 - Pain
 - Bleeding
- Less Likely and not serious:
 - Infection
 - Muscle cramps/spasms
- Less Likely and serious:
 - Bowel Perforation
 - Transient vasovagal response to needling

Lidocaine Risks:

- Likely and not serious:
 - Pain
 - Bleeding

- Less Likely and not serious:
 - Infection
 - Lidocaine toxicity

These risks will be minimized by cleaning the treatment site with an alcohol swab prior to placement. If at any time the patient reports a side effect, they will be referred to one of the Investigators for care. There may be a risk of inadvertent breach of confidentiality.

Costs: N/A

Safeguards for Protecting Information:

The research consents and HIPAA Authorization Documents will be stored in a locked cabinet in a locked room with restricted access. All identifiable research data including patient demographics will be kept in an electronic database separate from the coded research data, which will be encrypted, double password protected and the access will be restricted. The research data will be coded and any links to identifiable data (i.e., Master Key) will be destroyed as soon as all data mergers have occurred, or no later than at the closure of the study, all identifiable patient information will be destroyed based on AFI 33-332, "The Air Force Privacy and Civil Liberties Program" and the National Institute of Standards and Technology Special Publication (NIST SP 800-88) for the approved methods to destroy PII. The anonymized research data will not be utilized for further research activity beyond the protocol stipulations without additional IRB approval. At the conclusion of the study, the data will be de-identified prior to review and analysis.

Data and Specimen Storage Plan

How will coded or identifiable data/specimens be stored?

	Paper data, including completed consent forms	The research consents and HIPAA Authorization Documents will be stored in a locked cabinet in a locked room with restricted access.
	Electronic data	Medical records will be annotated with ICD-10 code Z00.6 to reflect the subject's participation in a research study, in which they are receiving a research-related treatment intervention. All research data that includes the Master Key of identifiable patient demographics and PHI/PII will be kept in an electronic database at each site, separate from the coded research data, which will be encrypted, password protected and the access will be restricted.
	Long-term storage (following completion of the study and inactivation of IRB approval)	The research data will be coded and any links to identifiable data will be destroyed (an approved shredding bin) as soon as possible or no later than at the closure of the study, with the exception of those study subjects that consent to place their de-identified research data into the "Nellis Acupuncture Research Data Repository (FWH20140048H)" for future research. The anonymized research data will not be utilized for further research activity beyond the protocol stipulations without additional IRB approval. All de-identified research data will be maintained for 3 years following study closure.

Safeguards for Protecting Subjects Relative to Reasonably Expected Risks:

Safeguards are in place for protecting subjects and their health data. The research consents and HIPAA Authorization Documents will be stored in a locked cabinet in a locked room. If at any time the patient reports a side effect, they will be referred to one of the Investigators for care.

Categories of subjects: None

Clinical Care:

All subjects will receive standard of care regardless of inclusion into this study. If at any time a subject experiences any injury or adverse effects, appropriate clinical care will be given or subject will be referred to appropriate provider.

Injury Compensation: N/A

Data Safety Monitoring:

N/A – none of the situations listed above apply

